Aim 2: Collect pilot data on the effects of ABMT and a PC task on levels of anxiety and impairment at a follow up evaluation 8 weeks after the post evaluation. This will provide initial data regarding the maintenance of ABMT effects 8 weeks after treatment ends. A multisource assessment approach will be used to preliminarily examine anxiety and impairment reduction among youth in the ABMT condition as compared to youth in the PC task condition at the 8 week follow up.

Aim 3: Preliminarily examine whether ABMT leads to lower levels of attention bias toward threatening stimuli as compared to a PC task at a post evaluation and at a follow up evaluation 8 weeks after post. Reductions in attention bias to threat have been theorized to mediate ABMT's anxiety reduction effect^{34,35}. Data from this UH2 will allow us to gain perspective on the theoretical underpinning of ABMT and will inform decisions about whether to pursue attention bias as a mediator in a subsequent R01.

Aim 4: Describe the course of anxiety symptoms and impairment during treatment among youth in the ABMT condition. Youth anxiety symptoms and impairment will be assessed at pre and every other session (i.e., sessions 2, 4, 6, 8), and post. We will explore the trajectory of anxiety symptoms and impairment across these six assessment waves in an effort to gain initial insight into 'dosage' related issues of ABMT.

APPROACH

See Figure 1 for the randomized, double blind, placebo controlled design. After a pre assessment, participants will be randomly assigned to either ABMT or Placebo Control (PC) Task.

In ABMT, participants will complete 8 sessions of ABMT. In PC, participants will complete 8 sessions of a PC task. Number and duration of sessions will be identical in both conditions. All participants will complete the Columbia Impairment Scale and Screen for Child Anxiety Related Emotional Disorders after even numbered sessions. A week after session 8, all participants will complete a post assessment. After post, no training or assessment will be administered for 8 weeks. Participants then will complete a follow up assessment. After the follow up, participants in the PC condition will be offered ABMT. All participants will be offered further treatment resources as needed (see Human Subjects). Total duration from pre to follow up will be ~12-14 weeks.

Participants. [66] youth (8-16 years) will be admitted.

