Treatment Conditions. Consistent with past ABMT trials^{76,77}, participants will complete 15-minute ABMT or PC task sessions 2X a week for 4 weeks. At each session, participants will complete 160 trials of either the ABMT task or the PC task. In both tasks, a fixation cross will appear first, followed by 2 faces of the same actor, one above the other. One face will depict the actor emoting an angry expression and the other will depict the actor emoting no expression. After presentation of the faces for 500ms, a probe (< or >) will appear in the location of one of the faces. Participants will indicate the type of probe (< or >) by pressing either the left or the right mouse button. The probe will remain on the screen until participants respond. After responding, the next trial will begin. **ABMT Task:** In this task, the probe will replace the neutral face on 100% of trials. On 80% of trials, angry face location will predict probe location (i.e., in the location opposite the angry face). On these trials, angry face location and actor will be fully counterbalanced. Probe type will appear with equal probability for angry face location and actor. On the other 20% of trials, participants will see neutral-neutral face pairs. **Placebo Control (PC) Task:** The PC task will be identical to the ABMT task except for the frequency with which the probe replaces the neutral face. 80% of trials include one neutral face and one angry face. On these trials, angry face location, probe location, and actor are fully counterbalanced. Probe type appears with equal probability for angry face location, probe location, and actor. The other 20% of trials include neutral-neutral face pairs. The PC task is an ideal control condition because it is robust to differential expectancy effects⁸⁴.

Measures. See Figure 1 for the assessment schedule. Each assessment will be conducted in single sessions at our clinics by carefully trained graduate research assistants.

I. Primary Outcome: Pediatric Anxiety Rating Scale (PARS)⁹³. The PARS is a widely used, reliable, and valid measure of global anxiety symptoms and impairment in youth ages 6-17. At the pre assessment, the interviewer who conducts the ADIS-C/P and PARS interviews will complete the rating. At post and follow up, an independent evaluator blinded to the patient's treatment condition will complete the PARS.

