Aim 1: Preliminarily examine whether levels of anxiety and impairment at post are lower for youth in ABMT as compared to youth in PC. The OLS analysis is a 2 group single degree of freedom contrast between the ABMT and the PC conditions using pre scores as a covariate to increase statistical power. The contrast focuses on the comparison of adjusted means at post. Of interest is whether the contrast between conditions is statistically significant for independent evaluator rated anxiety symptoms and impairment (PARS; **Primary Outcome**), parent ratings on youths' anxiety symptoms (SCARED-P) and impairment (CIS-P) (**Secondary Outcome**), and youth self ratings on anxiety symptoms (SCARED-C) and impairment (CIS-C) (**Secondary Outcome**).

Aim 2: Preliminarily examine whether levels of anxiety and impairment at 8 week follow up are lower for youth in ABMT as compared to youth in PC. The analytic approach will be identical to Aim 1, except that contrasts will focus on scores at the follow up evaluation instead of the post evaluation.

Aim 3: Preliminarily examine whether ABMT, as compared to PC Task, leads to lower levels of attention bias to threat at post and follow up. The analytic approach will be identical to Aims 1 and 2, except that contrasts will focus on scores on the attention bias task instead of scores on anxiety symptoms and impairment.

Aim 4: Describe the course of anxiety symptoms and impairment during treatment among youth in the ABMT condition. Youth anxiety symptoms and youth impairment will be assessed at pre, ABMT sessions 2, 4, 6, 8, and post. These 6 assessments waves can be used to gain insight into the timing of ABMT response. This analysis will be approached from a latent growth modeling framework. In separate analyses, we will model the trajectory of anxiety symptoms (SCARED-C/P) and impairment (CIS-C/P). Models of no growth, linear change, and quadratic change will be explored in an effort to identify the best fitting trajectory. We will use growth modeling variants that are amenable to small sample sizes¹⁰⁸.

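### Aim 4 names three growth shapes over six waves but gives no time scores and no separate term for the session-free week before post, so a constant per-session effect can look like diminishing returns

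*Combined protocol and SAP*

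**What the plan says.** The Statistical Analysis Plan, Aim 4, lists the waves: "Youth anxiety symptoms and youth impairment will be assessed at pre, ABMT sessions 2, 4, 6, 8, and post". SCARED and CIS, youth and parent versions, are to be modelled separately by latent growth modelling, using variants suited to small samples. The candidate shapes are given in one sentence: "Models of no growth, linear change, and quadratic change will be explored in an effort to identify the best fitting trajectory".

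The purpose is worded in two ways. The list of aims in the protocol says the trajectory is explored "in an effort to gain initial insight into 'dosage' related issues of ABMT". The Statistical Analysis Plan speaks of the timing of response.

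The schedule is in two other places. Treatment Conditions: "participants will complete 15-minute ABMT or PC task sessions 2X a week for 4 weeks". Approach: the interim measures come after even-numbered sessions, and "A week after session 8, all participants will complete a post assessment".

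The plan does not state what numbers the growth factors load on (wave order, weeks or sessions completed), how long before session 1 the pre assessment falls, or any piecewise form.

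**The concern.** Four of the five intervals between waves contain two sessions each. The last contains none. A single line or parabola through all six waves has to fit both kinds of interval. If each session helps equally and nothing changes once training stops, the flat last segment pulls the linear slope down and bends the quadratic. The bend then appears inside the training period, where there is none. A reader interested in dosage could conclude that later sessions add less than earlier ones. None of the three listed shapes separates change during training from change after it.

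**Working it through.** **Schedule.** Two sessions a week for 4 weeks is 8 sessions. Waves: 1 (pre) + 4 (sessions 2, 4, 6, 8) + 1 (post) = 6, as the plan states. Sessions completed: 0, 2, 4, 6, 8, 8. Duration: 4 weeks of training + 1 to post + 8 to follow-up = 13 weeks, which agrees with "Total duration from pre to follow up will be ~12-14 weeks".

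**Test case.** Let improvement be proportional to sessions completed and unchanged after session 8, with the total set to 1: y = 0, 0.25, 0.50, 0.75, 1, 1. The true gain is 0.25 at each training step and 0 at the last.

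**Wave order, t = 0 to 5** (also the week count if pre is one week before session 2).
- Linear slope = Σ(t − 2.5)y / Σ(t − 2.5)² = 3.75 / 17.5 = 0.2143. Ratio to truth: 0.2143 / 0.25 = 0.857, so 14% low.
- Quadratic contrast (5, −1, −4, −4, −1, 5) applied to y: −0.25 − 2 − 3 − 1 + 5 = −1.25. The sum of squared weights is 84. The coefficient on t² is 1.5 × (−1.25 / 84) = −0.0223.
- Fitted gain per step = 0.2143 − 2 × 0.0223 × (step midpoint − 2.5) = 0.304, 0.259, 0.214, 0.170, 0.125.
- The residual sum of squares falls from 0.0298 (linear) to 0.0112 (quadratic), so the quadratic describes the mean curve better although the training response is a straight line.

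**Other codings of the same truth.** A positive quadratic coefficient below means flattening (symptom score as outcome).

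| Coding | Quadratic coefficient |
|---|---|
| Weeks, pre one week before session 2 | 0.0223 |
| Weeks, pre half a week earlier than that | 0.0087 |
| Weeks, pre one week earlier | 0 |
| Weeks, pre two weeks earlier | −0.0087 |
| Sessions completed (0, 2, 4, 6, 8, 8) | 0, fit exact |
| Pre to session 8 only (0, 2, 4, 6, 8) | 0, fit exact |

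With pre one week earlier the curvature vanishes, but the slope is 0.186 per week against a true 0.25 during training. A lead of one week makes the total 13 + 1 = 14 weeks, still within the stated range; two weeks makes 15, just outside it.

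Session coding also depends on what happens after session 8. If improvement continues evenly by week through post, session coding gives a quadratic of −0.0038, which bends the curve the other way.

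**How often the bend would be significant.** Assumptions, since the documents give no effect sizes, SDs or allocation ratio: 66 / 2 = 33 ABMT youth, SD of individual total change 0.5, wave-order coding. The normalised contrast is 1.25 / √84 = 0.136 per unit of total change D. Its SD is √(residual SD² + (0.136 × 0.5)²). The noncentrality is 0.136 × D × √33 / SD, with a two-sided t test at 0.05 on 32 degrees of freedom.

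| Total change (SD) | Residual SD 0.3 | 0.4 | 0.5 | 0.6 |
|---|---|---|---|---|
| 0.5 | 24% | 16% | 12% | 10% |
| 0.8 | 51% | 32% | 23% | 17% |
| 1.0 | 70% | 47% | 33% | 24% |

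Simulation (4,000 runs per setting, residual SD 0.4 to 0.6) gave rates close to these. With session coding, or with post left out, its rejection rate was about 4 to 6%.

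**The case against.** A reader might infer that the plan treats post as one more step of exposure, and that model selection will therefore favour a quadratic. The documents support neither. They name shapes, not time scores, and the plan's own linear model on sessions completed fits the test case exactly. The quadratic is significant in more than half of trials in only 2 of the 12 settings above. The t test also only stands in for the plan's best-fit selection, whose criterion is not stated.

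It is also fair to say that Aim 4 is descriptive. On a time axis, a curve that flattens once training ends is an honest description. It misleads only if read as dose, and the plan sets no decision rule that does so.

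Finally, every ABMT participant is scheduled to train twice a week, so sessions and weeks are collinear up to session 8. Regression to the mean or repeated testing could bend the five training waves too, and recoding cannot rule that out.

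All of this limits the claim. What remains is that the choice of time scores decides the answer, the plan leaves it open, and each single-curve coding is safe only under a condition that the plan does not establish. For session coding, nothing may change after session 8. For calendar time, the curvature depends on the gap between pre and session 1.

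**Conclusion.** The concern holds as a gap in specification. The six waves are not equally spaced in training received, time scores are unstated, and no listed shape isolates the session-free week. Under wave-order coding, or weekly coding with pre one week before session 2, a constant per-session effect with no later change gives a slope 14% too low and training-step gains that appear to fall from 0.30 to 0.17 of the total. The chance of significant false curvature is about 10 to 70% over assumed effects of 0.5 to 1.0 SD and residual SDs of 0.3 to 0.6, and below one half in most of those settings. Its size and sign change with calendar coding.

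The documents do not show that the sponsor will code the waves this way or will draw a wrong conclusion about dosage. Severity is minor: the aim is exploratory, uses one arm, and touches neither the primary outcome nor any between-arm contrast.

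**What to change.** In the Statistical Analysis Plan, Aim 4:

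- State the time scores. Use sessions completed for the growth factors: linear loadings 0, 2, 4, 6, 8 from pre to session 8, held at 8 for post.
- Add one parameter for the change from session 8 to post (loading 1 at post, 0 elsewhere).
- Choose between no growth, linear and quadratic on the five waves from pre to session 8.
- Repeat with actual assessment dates as a sensitivity analysis, and report the interval from pre to session 1.
- State that sessions and weeks are collinear within the ABMT arm, so the curve describes course during training and does not by itself identify a dose effect.

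This needs changed loadings and a few sentences, with no new visits or data. The price is one extra mean parameter in a sample of about 33, and curvature judged on five waves instead of six.
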